VAs' lack of systematic and comprehensive S&R for unmet needs also means missed opportunities to better understand the scope and scale of unmet needs across the entire VA patient population, as no such data exists.¹⁴ This in turn limits VA's understanding of how best to support and target SW services. It is also unknown whether a lower-intensity referral process (i.e., provision of tailored paper Resource Sheets to address unmet needs instead of a referral to SW) can help some Veterans to the same extent it helps patients in non-VA care settings.

^{10, 16} Thus, a critically important dimension of the study we propose is to test whether for some Veterans, a less intense intervention is adequate. If so, this has valuable implications for resource allocation decisions and future implementation.

To address these knowledge gaps, we propose a **randomized controlled trial (RCT)** to systematically screen Veterans with/at risk for CVD for nine unmet needs, characterize the prevalence of unmet needs and associations with outcomes, and compare the effect of two different intensity referral interventions. Our primary outcome is Veterans' connections to new resources to address unmet needs. Additional outcomes include unmet need reduction, adherence (medications, ambulatory care appointments), utilization (preventable hospitalizations, urgent care), and clinical outcomes (blood pressure, glycemic control).

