Statistical Power for Aim 1: With a sample of N=1760 Veterans completing the index unmet needs screening, we will have 80% power to detect small effect sizes ($f^2=.01$; $OR=1.47$) using 2-tailed significance tests at the $\alpha=.001$ level if the intraclass correlation coefficient (ICC) (for the nesting of patients within sites) is negligible, or medium effect sizes ($f^2=.15$; $OR=4.07$) even if the ICC is as high as .02 for testing associations between the presence of each unmet need and sociodemographic, adherence, utilization, and clinical (BP only) variables. HbA1c is anticipated to be a relevant clinical outcome for only 40% of the sample; for HbA1c, we will have 80% power to detect small effect sizes ($f^2=.03$; $OR=1.84$) using 2-tailed significance tests at the $\alpha=.001$ level if the ICC is negligible.

Statistical Power for Aim 2: The power analysis for Aim 2 focused on the primary outcome of connection to resources to address unmet needs. The sample size was determined based on previous research outside VA which found that individuals who completed a screening and referral intervention were 15% more likely (adjusted Odds Ratio (aOR)=2.1) to have enrolled in a new community resource to address unmet needs post-referral compared to patients in the non-intervention arm. In the present study, we will have 80% power to detect an effect of this size (aOR=2.1) across the three arms using 2-tailed significance tests at the $\alpha=.05$ level, even if we assume an attrition rate as high as 50% for the follow-up phone call at 8-weeks post-screen (retained N=440 across all sites and arms) and a conservative ICC value for patients nested within sites of .01. Previous empirical work found ICC values <.0001 when adjusting for a small number of covariates (e.g., race, marital status) to examine new connections to resources to address unmet needs; we intend to collect and use these covariates in the present study as well. Assuming an ICC value of .0001, we will have 80% power to detect an effect as small as an aOR=1.7 if we assume a 50% attrition rate for the 8-week follow-up phone call, or as small as an aOR=2.0 if we assume a 70% attrition rate. We based our attrition rate upon the study team's prior study where Veterans

had low incomes, high unemployment and low educational status, yet only 35% were lost to a follow-up interview.

Quantitative Data Analysis

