Unmet Need Reduction: Similar analyses will be used to examine differences across our three study arms in change from baseline in the proportion of unmet needs among the sub-sample of participants who complete the re-screening at 6-months post-referral. Among this sub-sample (N=220, assuming attrition rates of 50% at both the 8-week and 6-month follow-up phone surveys), we will have 80% power to detect a small-to-medium effect ($f^2=.09$; OR=2.94) across the three arms in terms of unmet need reduction using 2-tailed significance tests at the $\alpha=.05$ level, even if we assume a conservative ICC value for patients nested within sites of .01.

Differences in Intervention Effectiveness. In addition to examining how the S&R influences connection to new resources, we will conduct additional analyses to examine whether there is differential impact between the two referral arms (Awareness and Assistance) on connection to new unmet needs resources; unmet need reduction; and adherence, utilization and clinical outcomes among Veterans with certain unmet needs or with fewer unmet needs. While we predict that providing SW support (Assistance arm) will generally have a larger impact on outcomes than providing a Resource Sheet alone (Awareness arm), it would be beneficial to know if the Resource Sheet alone (or even the screening and

provision of generic list of resources) is sufficient to produce comparable changes in outcomes among Veterans with certain unmet needs or among Veterans with fewer unmet needs. If true, future implementation research could create tailored interventions that funnel the resources for more time- and cost-intensive referral strategies to only those Veterans who need it most.

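### Section 5.6 asks whether a lower-intensity arm is sufficient in subgroups, but names only an analysis of differential impact and sets no criterion for comparable

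*Combined protocol and SAP*

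**What the plan says.** The Introduction (2.0) says that "a critically important dimension of the study we propose is to test whether for some Veterans, a less intense intervention is adequate". It adds that, if so, "this has valuable implications for resource allocation decisions and future implementation".

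The matching analysis is in 5.6 under Differences in Intervention Effectiveness. The team will "examine whether there is differential impact between the two referral arms (Awareness and Assistance) on connection to new unmet needs resources", and likewise on need reduction, adherence, utilization and clinical outcomes, among Veterans defined by type or number of needs. The section then says it would help to know whether the Resource Sheet alone, or even screening with the generic list, "is sufficient to produce comparable changes in outcomes among Veterans with certain unmet needs or among Veterans with fewer unmet needs". A positive answer is expected to feed later implementation research that reserves the costlier support for those who need it most.

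Every Aim 2 power statement in 5.6 concerns a two-tailed significance test. For this question the documents give no margin, no confidence-interval rule, no definition of *comparable* or *sufficient*, no cut-off for fewer needs, and no subgroup power.

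**The concern.** Sufficiency and difference are separate questions. To say that a cheaper arm is good enough, the data must exclude a deficit large enough to matter. A test of difference that comes out non-significant does not do that, least of all in part of a sample that is expected to lose half its members by 8 weeks.

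The plan poses the first question and describes only an analysis suited to the second. A report could follow the plan to the letter and still present a null subgroup result as showing that Resource Sheets are enough for certain needs. Because the Introduction links the answer to how resources are allocated, an error in that direction could count against social work support for Veterans who gain from it.

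**Working it through.** **Inputs from the documents.** 880 randomised 1:1:1 and 440 retained at 8 weeks, so 440/3 = 146.7 per arm; 220 retained at 6 months; two-tailed α = .05; 65% follow-up in the team's prior study (all 5.6). Participants are taken as randomised individually within site (5.1, Appendix A), so no cluster inflation is applied.

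**Assumptions, not in the documents.** A 30% connection rate in Awareness, and subgroups holding 50% or 30% of the sample.

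**The plan's own figure.** The planning study's participants "were 15% more likely (adjusted Odds Ratio (aOR)=2.1) to have enrolled in a new community resource". Reading 15% as percentage points, p₁ = p₀ + .15 with OR 2.1 gives 1.1p₀² − .935p₀ + .15 = 0. The lower root is p₀ = .215, p₁ = .365. For one pair of arms with n = 146.7:

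Power = Φ[(.15 − 1.96·√(2·.290·.710/n)) / √((.215·.785 + .365·.635)/n)] = Φ[(.15 − .104)/.0522] = 81%.

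This matches the stated 80%. On this reading, the figure is power to detect a whole-trial difference between two arms.

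**Subgroup precision and miss rates.**

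- Half-width (equal rates) = 1.96·√(2·.3·.7/n)
- P(non-significant) = Φ(1.96 − δ/SE) − Φ(−1.96 − δ/SE), with SE = √[(.3·.7 + (.3+δ)(.7−δ))/n]

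| Case | n per arm | 95% CI | δ = 7.5 points | δ = 10 | δ = 15 |
|---|---|---|---|---|---|
| 440 responders, 50% subgroup | 73.3 | ±14.8 | 84% | 75% | 52% |
| 440 responders, 30% subgroup | 44.0 | ±19 | 88% | 83% | 69% |
| 65% retained (572), 50% subgroup | 95.3 | ±13.0 | 80% | 69% | 42% |

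Example: n = 73.3, δ = .10: SE = √(.45/73.3) = .0783; δ/SE = 1.28; Φ(.68) − Φ(−3.24) = 75%.

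**Sensitivity to the rate.** With n = 73.3 and δ = 10 points, Awareness rates of 20% to 50% give 71% to 77%; a 10% rate gives about 60%.

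**The protocol's own prediction.** Section 5.6 expects Awareness to lie between the other arms. Placed midway on the log-odds scale (an assumption), the odds ratio against Assistance is √2.1 = 1.45, or 28.4% v 36.5%, a gap of 8.1 points. In a half-sample this is non-significant 82% of the time.

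**Six months.** A half-sample of 220 is 36.7 per arm. Using the same 30% rate only for illustration, the half-width is ±21 points and a 15-point deficit is missed about 73% of the time.

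**Outcomes analysed on N = 880.** P(miss) = 1 − Φ(d·√(n/2) − 1.96). In a half-sample (n = 146.7) a 0.2 SD difference is missed 60% of the time and a 0.3 SD difference 27%.

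**What a margin-based rule could show.** If the arms are truly equal at 30%, P(CI excludes margin m) = Φ(m/√(2·.3·.7/n) − 1.96):

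| Margin | Half-sample (73.3) | Whole trial (146.7) |
|---|---|---|
| 7.5 points | 17% | 29% |
| 10 points | 26% | 46% |
| 15 points | 51% | 80% |

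**Interaction.** For a 50/50 split at the planning rates, each half contributes variance (.169 + .232)/73.3 = .00546. The difference in arm effects detectable with 80% power is 2.80·√(2·.00546) = 29 points.

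**The case against.** The strongest reply is that the plan never says a null result will be read as adequacy. A reader might infer that it will, and that the trial is therefore set to produce false claims of sufficiency. The documents do not support that: 5.6 gives no decision rule in either direction. What stands is that the criterion is missing and the inference is left open.

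The stakes can also be overdrawn. Section 5.6 presents these as further analyses whose next step is research, and it claims no power for them, so no stated figure is wrong. That limits the severity. It does not remove the point, because 2.0 gives the question weight and names resource allocation.

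The wording on differential impact can be read as effect modification within the hierarchical models, and separate subgroup tests are not specified. That is fair, and part of the remedy may already be intended. The Data Analysis Plan mentioned in 5.1 may say more, but it cannot be checked here. An interaction test still does not define *comparable*.

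On size, 50% retention is deliberately conservative. At 65% the half-sample interval falls inside 15 points and a full 15-point deficit is missed 42% of the time. A reader might infer that non-significance is the usual result whatever the true deficit. It is not: for a 15-point deficit in a half-sample it is close to even, and for larger effects on the N = 880 outcomes it is the less likely result.

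**Conclusion.** The point holds as a gap between question and method. The plan asks about sufficiency, names an analysis of difference, and sets no criterion for *comparable*. For the survey outcomes, the subgroups cannot support a conclusion of adequacy from non-significance. In a half-sample at the planned retention, the interval is about as wide on each side as the 15-point planning effect, and moderate deficits of 7.5 to 10 points are missed 75% to 84% of the time. At 65% retention this is 69% to 80%. These figures rest on an assumed 30% rate, assumed subgroup shares, and 15% read as percentage points. The rate matters little between 20% and 50%. The problem is milder for larger effects on adherence, utilization and clinical outcomes. This is a change the sponsor should make; it does not affect the primary comparison.

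**What to change.** In 5.6, under Differences in Intervention Effectiveness:

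- State that a non-significant difference will not be read as *sufficient* or *comparable*.
- Assess arm-by-need and arm-by-number-of-needs interactions in the full model.
- Report Assistance minus Awareness, and Assistance minus Screening, with 95% CIs in each subgroup, labelled exploratory. The second contrast is needed because 5.6 also asks about screening with the generic list.
- Use *sufficient* or *comparable* only for an outcome whose CI excludes a deficit larger than a margin that the sponsor fixes and justifies for that outcome before outcome data by arm are examined. Otherwise report *not established*. The time point is set this way because the documents describe no blinding: the RA opens the envelope and tells the participant the assignment (Appendix A).

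The cost is wording, a margin to justify for each outcome on which such a claim may be made, and some extra intervals; no more participants are needed. The downside is that most subgroups will be reported as inconclusive. As the working shows, even with truly equal arms a 10-point margin would be met about 26% of the time in a half-sample, and the interactions will detect only large differences. That is what the sample can support.

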5.5 Study Evaluations

RCT participants will be asked to complete three brief surveys over a 6-month period. A small sub-set of participants will additionally be invited to participate in qualitative interviews.

Index Unmet Need Screen (survey #1): We will assess unmet needs among trial participants based on the index screen (administered prior to randomization). See **Appendix I** for the Index Unmet Need Survey.

Eight-Week Follow-Up Survey (survey #2): Eight weeks after the index screen, the RA will conduct phone follow-up with each Veteran to assess if they connected to any new resources in the intervening time and if so, to which one(s). See **Appendix J** for the Eight-Week Follow-Up Survey and accompanying phone script.

6-Month Unmet Need Re-Screen (survey #3): Six months after the index screen and by phone, the RA will re-administer the unmet need survey modified slightly

to exclude questions related to preferences for assistance (see **Appendix K** for the Six-Month Unmet Need Survey and accompanying phone script). We will define unmet need reduction in two ways: 1) one or more of baseline unmet needs no longer identified as an unmet need at the 6-month re-screen; and 2) percentage of baseline needs not reported as unmet needs at 6-month rescreen.

Qualitative Interviews with Veterans: Among study participants, we will purposefully select and recruit 60 Veterans to participate in qualitative interviews. The interviews are designed to understand the conditions that facilitate or impede a Veteran connecting to resources, as well as the conditions under which resources do or do not address a Veteran's needs. The RA at each study site will conduct the interviews. See **Appendix L and M** for the Veteran Interview Guides and accompanying phone scripts).

Qualitative Interviews with Representatives of VA and Community Resources: To understand how VA- and community-based programs experience the intervention, we will interview a purposeful sample of the VA- and community-based programs that trial participants used as a result of the intervention. The RA at each study site will conduct the interviews. See **Appendix N** for the Resource Representative Interview Guide and accompanying phone script.

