Testing Conceptual Path. To the extent that we discover differences across intervention arms in any of our more distal outcomes, we will conduct exploratory analyses to test appropriate causal mediational paths as proposed in our conceptual model using a series of HLM/HGLM analyses (with patients nested within sites). That is, we will examine whether the impact of our intervention on more distal outcomes (e.g., BP) can be explained completely (or in part) by its impact on more proximal outcomes (e.g., connection to new resources, reduction in unmet needs). For example, if we find differences across study arms in reduction in unmet needs, we will test whether the effect of the intervention arm on reduction in unmet needs is mediated by the effect of the intervention arm on connection to new resources.

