Appendix J: Eight-Week Follow-Up Survey

Phone Contact:

Hello, my name is _____, I'm calling from the (Name of VAMC). I am trying to reach [Name of Veteran].

Not Present: I'll call back another time, thank you. Is there a good time to try calling back?

Voicemail: Hello, my name is [name of research team member], I am calling from the (Name of VAMC). I wanted to speak with [Name of Veteran] about the Resource Needs Study. It's time to complete one of the brief questionnaires that are part of this study, it will only take about 5 minutes to complete. Please contact me at [name]. If you get my voicemail please leave your name, the best number to reach you at, and the most convenient times to reach you. Thank you.

Present: Hello, my names is [name of research team member] and I work at the (Name of VAMC). I wanted to speak with you about the Resource Needs Study you are participating in. It's time to complete one of the brief questionnaires that are part of this study, it will only take about 5 minutes to complete. Do you have a few minutes now?

If No: When is a good time for you to answer some questions about your social circumstances? (*SCHEDULE A TIME AND CONFIRM BEST CONTACT NUMBER*)

If Yes: Great, let's get started.

Screening Survey

1. Since we last talked on [insert index screening date], were you able to connect with any new programs or services for help with [insert needs identified from index screen)?

Yes

No (skip to Q5)

2. Which programs or services did you connect with?

3. Were you able to get the help you wanted from this (these) program(s)?

Yes

No

4. How did you connect with this (these) program(s)?

Probes

phone call

walk in

web-based

e-mail

5. Why were you unable to connect with the [insert specific resources that were provided to respondent at index screen, e.g., food, employment] programs(s)?

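### The exploratory mediation test of arm, connection and need reduction names no adjustment for the number of index needs, so its connection-outcome step is biased for some of the planned need-reduction measures

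*Combined protocol and SAP*

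**What the plan says.** Section 5.6, Testing Conceptual Path, applies when arms differ on a distal outcome. It states that "we will conduct exploratory analyses to test appropriate causal mediational paths", by multilevel models with patients nested within sites. Its worked example is need reduction: "if we find differences across study arms in reduction in unmet needs", then "we will test whether the effect of the intervention arm on reduction in unmet needs is mediated by the effect" of arm on connection. It names no covariates, no common causes of connection and need reduction, and no sensitivity analysis.

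The measures are defined elsewhere:

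- **Mediator.** Appendix J, question 1, at eight weeks: "were you able to connect with any new programs or services for help with" the needs identified at the index screen. It is a single yes/no.
- **Outcome, Section 5.5.** There are two definitions: "one or more of baseline unmet needs no longer identified as an unmet need at the 6-month re-screen", and "percentage of baseline needs not reported as unmet needs at 6-month rescreen".
- **Outcome, Section 5.6, Unmet Need Reduction.** "change from baseline in the proportion of unmet needs among the sub-sample" of re-screened participants, with no denominator given.

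Covariates such as race and marital status are mentioned in the Aim 2 power paragraph, for the connection outcome. Prior resource use is controlled in supplemental analyses of intervention effects. The number of needs appears in Section 5.6 only as a possible modifier of effect (Differences in Intervention Effectiveness).

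**The concern.** Randomisation protects the comparison of arms. It does not protect the comparison, within arms, of Veterans who connected with Veterans who did not. Without adjustment, that step tests whether connection and need reduction are associated given arm, which differs from whether connection has an effect.

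Here a specific common cause is visible. A Veteran with three needs has more chances to answer yes about connecting for any of them, and more chances that at least one need is gone at six months, even if connecting does nothing. The index screen records the number of needs before randomisation, but the plan does not put it into these models. At stake is the statement that connection is what carries the arm's benefit, which is the first link in the sequence H1 describes.

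**Working it through.** **1. The plan's own figures.** Sample: 880 × 0.5 × 0.5 = 220, as stated. The stated power for need reduction is 80% at f²=.09 with ICC .01. With three sites the design effect is 1 + (220/3 − 1) × .01 = 1.723, so the effective N is 220/1.723 = 127.7 and the noncentrality is .09 × 127.7 = 11.5. Power is 80.9% with 3 numerator df and 86.0% with 2 df, so the figure reproduces in the 3-df form. The plan states no power or error rate for the mediation test.

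**2. Number of needs (assumption anchored to the plan).** The sample-size text gives 50% (planning) and 78% (pilot) with at least one need. If nine needs are independent with common chance p, then p = 1 − 0.5^(1/9) = .074 or 1 − 0.22^(1/9) = .155. The mean number k among those with a need is 9p/0.5 = 1.33 or 9p/0.78 = 1.79. A wider spread (mean 3.46) was also run, because needs may cluster.

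**3. Why k matters.** Suppose each need resolves with chance q = .30 whatever k is:

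| Measure | Formula | k=1 | k=2 | k=3 |
|---|---|---|---|---|
| One or more gone | 1 − (1−q)^k | .30 | .51 | .66 |
| Change out of nine | qk/9 | .033 | .067 | .100 |
| Percentage of baseline needs | q | .30 | .30 | .30 |

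The chance of any connection, 1 − (1−c)^k, also rises with k if each need offers a separate chance c. The third measure does not move with k.

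**4. Simulation with connection inert** (1,000 trials per setting, simulation error up to about 1.6 points). Connection is 22/29.5/37% by arm, close to the plan's 15-point difference and aOR 2.1, which together imply about 21% v 36%. Site is a fixed effect. The table gives two-sided rejection of the connection coefficient given arm; nominal is 5%.

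| Setting | One or more gone | Out of nine | Percentage of baseline |
|---|---|---|---|
| N=220, mean k 1.33-1.79 | 10-24% | 18-48% | 2-5% |
| N=440, mean k 1.33-1.79 | 18-39% | 30-74% | 2-5% |
| N=220 or 440, mean k 3.46 | 59-90% | 85-100% | 2-5% |
| Any of these, k added (1 to 5+) | 5-6% | 6-13% | 2-5% |

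Separate runs at N=220 with anchored need counts gave 12-21% and 25-48% unadjusted and 4-7% adjusted. The adjusted range overall is therefore about 4-13%.

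**5. A complete false claim.** The plan states no decision rule. The rule assumed here requires a significant arm difference in reduction, a significant arm difference in connection, and a significant positive connection coefficient given arm.

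- *Arm has no effect on reduction:* 0-3.5% in every setting.
- *Arm acts by another route* (resolution .30/.40/.50, assumed), N=220, anchored k: 2-6% (one or more gone) and 6-15% (out of nine). Separate runs with a direct log-OR of .8 and Screening connection of 25% gave 4-8% and 8-16%, so the upper ends are approximate.
- *Same, N=220, mean k 3.46:* 15% and 36%.
- *Same, N=440:* 12-59% and 29-74% across the need-count spreads.
- *Percentage of baseline needs:* at most 2.1% in all of these.
- *With k added:* at most 2.8% (one or more gone) and 8.2% (out of nine).

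**6. The bias can reverse.** If needs resolve less often when there are many (mean k 3.46), the percentage measure shows a false association in 38% (N=220) to 69% (N=440) of trials, essentially all negative. Adding k returns this to about 4%.

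**The case against.** A reader might infer that the plan would often declare mediation when connection does nothing. The documents do not support that. The analysis is labelled exploratory and runs only after an arm difference appears. With no arm effect, the gate holds false claims to 3.5% or less. Frequent false claims need an arm effect by another route together with a larger N or a wider spread of needs than the planning figures suggest. N=440 is the plan's eight-week number; its figure for need reduction is 220.

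The Section 5.6 outcome may simply be the percentage-of-baseline measure, which shows no inflation. Dividing by nine is one reading of an unstated denominator. The link between connection and need count is also an inference from the survey item, since Veterans with many needs might connect less.

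A reader might also extend the error to the blood pressure, adherence and utilization paths, or assume that it always favours the hypothesis. Those outcomes have no mechanical link to need count and were not calculated, and step 6 shows that the sign can reverse.

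These points limit the size of the problem but do not supply an adjustment. Mediation is interpreted only once the gate opens. Among trials passing it at N=220, with connection inert and a direct arm effect, false claims were 6-18% (one or more gone) and 12-28% (out of nine), over the anchored counts and a uniform 1-6 spread. A direct route is credible: Appendix A gives the Assistance arm motivational interviewing, an action plan and repeated calls, and loneliness and stress are among the screened needs. N could also exceed 220: the prior study's 65% follow-up, applied twice, gives 880 × .65 × .65 ≈ 372.

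**Conclusion.** The concern holds in limited form. As written, the connection-outcome step of the mediation test does not hold its nominal level for one of the two Section 5.5 definitions, nor for the Section 5.6 wording if the denominator is nine. At N=220 with anchored need counts, rejection is roughly 10-24% and 18-48% when connection has no effect. The percentage-of-baseline measure is not inflated by construction, though it can be biased the other way.

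A full false mediation claim is less common: about 2-6% or 6-15% at N=220 given an arm effect by another route, higher with larger N or wider need counts, and at most about 3.5% if the arm does nothing. The primary comparison is untouched.

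These sizes rest on assumptions outside the documents: the need-count distribution, independence of needs, resolution rates, a separate chance of connection per need, the size of the direct arm effect, and the decision rule. The absence of a stated adjustment set does not depend on them.

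**What to change.** In Section 5.6, Testing Conceptual Path:

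1. Include the number of index needs, as categories, in both the connection model and the outcome model. Merge sparse upper categories.
2. Name the percentage of baseline needs no longer reported as the need-reduction outcome for mediation, and state the denominator. Keep the adjustment, because this measure can still be biased if resolution depends on the number of needs.
3. Add a sensitivity analysis for remaining confounding of connection and outcome. Adjusting for need count alone does not make the estimate causal.
4. Report the result as mediation conditional on those assumptions.

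The cost is a wording change, a few degrees of freedom (four indicators for categories 1 to 5+), one added sensitivity analysis, and a less decisive statement. The need count comes from the index screen, which is completed before randomisation, so no new data are required.
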